6.5.3 Analysis of secondary endpoints

In the analysis of secondary endpoints, continuous variables will be described using the mean \pm standard deviation or the median (interquartile range); categorical variables will be described using counts (percentages). Missing values for secondary endpoints will neither be imputed nor subjected to sensitivity analysis.

Secondary endpoints:

Variables	Type	Effect size	P value
Urinary tract infection	categorical variable: no, yes	Absolute risk difference (95% CI)	*.***
The time from catheter removal to the first micturition	continuous variable: hours	Difference (95% CI) by Hodges-Lehmann method	*.***
Catheter-related bladder discomfort (CRBD)	categorical variable: level 0, level 1, level 2, level 3	Absolute risk difference (95% CI)	*.***
ICIQ-SF score on the second day after the first removal of the urinary catheter	continuous variable: points	Difference (95% CI) by Hodges-Lehmann method	*.***

ICIQ-SF classification on the second day after the first removal of the urinary catheter	categorical variable: no or mild, moderate, severe	Absolute risk difference (95% CI)	*.***
IPSS score on the second day after the first removal of the urinary catheter	continuous variable: points	Difference (95% CI) by Hodges-Lehmann method	*.***
IPSS classification on the second day after the first removal of the urinary catheter	categorical variable: mild, moderate, severe	Absolute risk difference (95% CI)	*.***
Surgical Complications within 30 days after surgery	categorical variable: no, yes	Absolute risk difference (95% CI)	*.***
Specific types of complications	categorical variable: no, yes	-	-
.....	-	-
Clavien - Dindo Classification of Surgical Complications \geq III	categorical variable: no, yes	Absolute risk difference (95% CI)	*.***
Bladder residual urine volume $>$ 200 ml after the first voiding	categorical variable: no, yes	Absolute risk difference (95% CI)	*.***

Other outcomes of interest:

- Self-assessment form on the quality of bladder training, presented in the form of a bar chart.
- Postoperative hospital stays, continuous variable, measures in days;
- Duration of urinary catheter indwelling, categorical variable: within 1 day, 2 days, \geq 3 days;
- Time from catheter removal to second catheterization, categorical variable: within 1 day, 2 days, \geq 3 days;
- Volume of first urination after surgery, continuous variable, measures in milliliters;
- Methods of second catheterization, categorical variable: indwelling urinary catheter, indwelling suprapubic puncture tube;
- Volume of urine drained by the second catheterization, continuous variable, measures in milliliters;
- Pathological outcomes, include:
 - Tumor volume, continuous variable, measures in cm^3 ;
 - Circumferential Resection Margin (CRM) distance, continuous variable, measures in millimeters;
 - Positive CRM rate, categorical variable: negative, positive;

- Distal Resection Margin (DRM) distance, continuous variable, measures in millimeters;
- Positive DRM rate, categorical variable: negative, positive;
- Pathological stage T, categorical variable: pathological complete response (pCR), Tis, T1, T2, T3, T4;
- Pathological stage N, categorical variable: N0, N1, N2;
- Pathological stage TNM, categorical variable: 0 stage, I stage, II stage, III stage, IV stage;
- Number of harvested lymph nodes, continuous variable, measures in piece;
- Number of metastatic lymph nodes, continuous variable, measures in piece.

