2.2 Study Endpoint

2.2.1 Primary Study Endpoint and Definition

The primary endpoint of the study is urinary dysfunction in patients within 7 days after catheter removal. In this study, urinary dysfunction was defined as incomplete bladder emptying after the first voiding following catheter removal or an inability to urinate requiring a second catheterization.

Incomplete bladder emptying was characterized by a postvoid residual urine volume (PRUV) exceeding 100 mL (14–18). The residual urine volume in the bladder after the first urination will be estimated immediately following the first urination using bladder ultrasound. The calculation formula is: Bladder urine volume = Anteroposterior diameter * Vertical diameter * Transverse diameter * 0.52. The bladder ultrasound is performed by a fixed radiologist from the ultrasound imaging department, who is exclusively assigned to our department.

The criteria for determining whether secondary catheterization is needed due to difficulty in urination are as follows: 1)The patient is unable to urinate within 10 hours after catheter removal, and percussion of the bladder upper border indicates that it is located above the pubic bone, with an estimated residual urine volume in the bladder greater than 200 ml using bedside bladder ultrasound; 2)Although the patient is able to urinate after catheter removal, they still feel lower abdominal distension after multiple attempts to urinate, and percussion by the physician indicates that the bladder upper border is located above the pubic bone, with an estimated residual urine volume in the bladder greater than 200 ml using bedside bladder ultrasound.

In the determination of the primary endpoint, patients who undergo secondary catheterization for reasons other than urinary retention will also be recorded as primary endpoint events, but sensitivity analysis shall be conducted on these patients in the sensitivity analysis. The specific analysis method is described in the section on sensitivity analysis of the primary endpoint in the statistical analysis. Such events may include the following scenarios:

- 1) The patient requests secondary catheterization due to urgent urination or intense bloating, but the urine volume withdrawn after secondary catheterization does not exceed 100 ml;

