- 2) The patient requires secondary catheterization due to disease-related factors (such as secondary surgery, urethral injury, shock, altered consciousness, intestinal obstruction, hemorrhage, transfer to ICU, SOFA score ≥ 2 , etc.).

2.2.2 Secondary study endpoints and definitions.

Secondary endpoints of this study include: 1) Catheter-associated urinary tract infection status; 2) Time to first urination after catheter removal; 3) Grading assessment of catheter-related bladder discomfort (CRBD); 4) Post-catheter removal urinary function evaluation (using ICIQ-SF and IPSS scores); 5) Postoperative complications within 30 days (incidence of complications, types of complications, and grading of complications); 6) Incidence of residual urine volume greater than 200 milliliters after the first urination.

2.2.3 Other indicators and definitions.

Urinary tract infection is defined as an inflammatory response of the urinary epithelium to bacterial invasion. The diagnosis requires both of the following criteria to be met: 1) Urinalysis indicates a bacterial count above the normal upper limit, and 2) Positive urine culture. The time to first urination after catheter removal is defined as the time from the removal of the catheter to the patient's spontaneous urination, measured in hours. The time from the second catheterization to the removal of the urinary catheter is defined as the time interval from the first removal of the urinary catheter to the completion of catheter insertion by the nurse or suprapubic puncture by the ultrasound doctor after the clinician determines that the patient requires a second catheterization.

Complications within 30 days after surgery are assessed according to the Clavien-Dindo classification, and complications of grade II and above are recorded and analyzed. These include, but are not limited to, intraperitoneal bleeding,

gastrointestinal bleeding, anastomotic leak, chylous fistula, surgical site infection (intra-abdominal infection and incisional infection), intestinal obstruction, postoperative diarrhea, pulmonary infection, urinary tract infection, cardiovascular accident, cerebrovascular accident, and thrombotic diseases.

3. Study design.

3.1 Overall study design.

Single-center, prospective, two-arm, parallel-group randomized controlled study.

3.2 Study duration.

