11.4.3 Analysis of secondary endpoints

In the analysis of secondary endpoints, continuous variables will be described

using mean \pm standard deviation or median (interquartile range); categorical variables will be described using counts (percentages). Missing values of the secondary endpoints will not be imputed, nor will sensitivity analyses be conducted for them.

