4.2 Secondary endpoints

The secondary endpoints of this study are as follows: 1) the incidence of urinary tract infections associated with the catheter, 2) the time to first void after catheter removal, 3) CRBD grade, 4) evaluation of voiding function after catheter removal using the ICIQ-SF and International Prostate Symptom Score (IPSS), 5) Evaluation of the incidence, type, and grade of complications within 30 days postoperatively, and 6) Incidence rate of residual urine volume greater than 200 ml after the first voiding.

5 Sample size

The sample size is calculated based on a differential test, with urinary dysfunction as the primary endpoint. Based on our preliminary research results, the incidence of urinary dysfunction in the bladder training group is 44.7%, and in the direct removal group, it is 59.3%. Patients are randomly assigned to the two groups in a 1:1 ratio. With a one-sided significance level α of 0.05 and a power (1- β) of 80%, the sample size was calculated using PASS 15 software. Each group, the bladder training group and the direct removal group, requires 180 cases. Assuming a dropout rate of 10%, each group requires 200 cases. Therefore, this trial needs a total of 400 cases.

6 Statistical methods

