If secondary catheterization does not occur within 7 days after the removal of the urinary catheter, and the post-void RUV by ultrasound after the second urination is also missing, handling method: Multiple imputation method is used to impute the missing data of the first post-void RUV.

4) When the data on post-void RUV by ultrasound after the first urination is missing, and the situation of secondary catheterization within 7 days after the removal of the urinary catheter is also missing.

If the post-void RUV by ultrasound after the second urination is not missing, handling method: The LOCF method is used to impute the missing data of the first residual urine volume. If the imputed residual urine volume is greater than 100 ml, the primary endpoint is reached (positive), and no imputation of missing data for secondary catheterization is performed; if the imputed residual urine volume is less than or equal to 100 ml, multiple imputation method is used to impute the missing data of secondary catheterization.

If the post-void RUV by ultrasound after the second urination is also missing,

handling method: Multiple imputation method is used to impute the missing data of the primary endpoint. At this time, the primary endpoint is imputed as a whole missing data, rather than imputing the RUV and secondary catheterization separately.

Through the above treatment methods, we will minimize the impact of missing data on the research results and ensure the accuracy and reliability of data analysis. The handling process of missing data in primary endpoint is shown in Figure 1.

In the analysis of secondary endpoint and subgroup analysis, we will not perform imputation of missing data.

Handling flow of missing data for primary endpoint

Both the RUV after the patient's first urination and the secondary catheterization data within 7 days after catheter removal are complete

No missing data, no processing required

The RUV after the patient's first urination is complete but the secondary catheterization data within 7 days after catheter removal is missing

The RUV after the first urination is >100 ml

The primary endpoint is achieved, and no imputation for missing data on secondary catheterization is required

The RUV after the first urination is ≤100ml

Multiple imputation method is employed to handle the missing data for secondary catheterization

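### Patients re-catheterised for retention before any void have no value for time to first urination or first-void residual, so two secondary endpoints are compared only among patients who voided

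*SAP*

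**What the plan says.** **Definitions.** Protocol v2.0, 2.2.3: "The time to first urination after catheter removal is defined as the time from the removal of the catheter to the patient's spontaneous urination". Sections 2.2.1 and 6.1.2 have the residual scanned straight after the first void. The added secondary endpoint in SAP 4.2 is "Incidence rate of residual urine volume greater than 200 ml after the first voiding".

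**Re-catheterisation.** The first criterion in Protocol 2.2.1 begins "The patient is unable to urinate within 10 hours after catheter removal". It also requires a bladder that percusses above the pubic bone and an "estimated residual urine volume in the bladder greater than 200 ml using bedside bladder ultrasound". The second criterion is for patients who have already voided.

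**Missing values.** SAP 6.5.3: "Missing values for secondary endpoints will neither be imputed nor subjected to sensitivity analysis". SAP 6.3.2 agrees: "In the analysis of secondary endpoint and subgroup analysis, we will not perform imputation of missing data". Protocol 11.4.3 adds "nor will sensitivity analyses be conducted for them".

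**Analysis.** The table in SAP 6.5.3 gives time to first void as a Hodges-Lehmann difference and residual above 200 ml as a no/yes variable with an absolute risk difference. It states no denominator for either.

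**Primary endpoint, for contrast.** Under SAP 6.3.2, a patient with a second catheter and no residual counts as an event.

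**The concern.** For a patient who meets the first criterion, the missing value is a consequence of the outcome: the patient could not void. The primary endpoint counts that patient as a failure. The two secondary endpoints have no rule for the patient, and imputation and sensitivity analysis are both excluded.

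The comparison then rests on voiders only. Failure to void is part of what ICCAUT is meant to change, so the voiders in the two arms need not be comparable. If ICCAUT prevents retention, the control arm loses more of its worst patients and the difference shrinks. If ICCAUT causes retention, these two rows understate the harm. Protocol v2.0 moved the primary analysis from modified ITT to ITT because of this kind of selection.

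**Working it through.** The plan states no figure for either secondary endpoint, so there is none to reproduce. The documents also give no rate of re-catheterisation before a void. The rates below are assumptions, except the ratio 0.754.

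**Inputs**
- Planned size: 200 per arm (SAP 5).
- Control non-voider share *c*: assumed 5% to 15%, with 2% as a low case.
- ICCAUT non-voider share *t* = *c* × ratio. Ratios are 1 (no difference), 0.754 and 0.5. The middle value is 44.7/59.3, from the composite event rates in SAP 5; applying it to non-voiding is itself an assumption.
- Share *v* of voiders above 200 ml: assumed 15% to 25%, equal in both arms.

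**Residual above 200 ml**
- Non-voiders left out: *v* − *v* = 0.
- Non-voiders counted as positive: [*t* + (1−*t*)*v*] − [*c* + (1−*c*)*v*] = (*t* − *c*)(1 − *v*).

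| Ratio | *c* | *t* | *v* = 25% | *v* = 15% |
|---|---|---|---|---|
| 0.754 | 5% | 3.77% | −0.9 | −1.0 |
| 0.754 | 15% | 11.31% | −2.8 | −3.1 |
| 0.5 | 5% | 2.5% | −1.9 | −2.1 |
| 0.5 | 15% | 7.5% | −5.6 | −6.4 |
| 1 | any | = *c* | 0 | 0 |

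(Differences in percentage points.) At *c* = 2%, ratio 0.754 and *v* = 20%, the result is −0.4. For scale, the 95% half-width at *v* = 20% is 1.96 × √(2 × 0.2 × 0.8/200) = 7.8 points.

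If an analyst instead coded non-voiders as no, the difference would be (*c* − *t*)*v*. At 10% vs 5% and *v* = 20% that is +1.0 point, the opposite sign to the −4.0 obtained by counting them.

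If voiders also differ (25% vs 18%) and non-voiders are 10% vs 5%, leaving them out gives −7.0 points (power 37%) and counting them gives −10.4 (power 65%). With 10% non-voiders in each arm, counting them gives 0.9 × (−7.0) = −6.3.

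**Time to first void** (simulated Mann-Whitney tests, 200 per arm; lognormal times, medians 4.0 h control and 3.2 h ICCAUT). About 9% vs 5% exceed 10 h at log-SD 0.7, and 15% vs 10% at log-SD 0.9.

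| Share of those beyond 10 h re-catheterised before voiding | Log-SD | Power, left out | Power, ranked last |
|---|---|---|---|
| All | 0.7 | 77% | 88% |
| All | 0.9 | 44% | 67% |
| Half | 0.7 | 83% | 88% |
| Half | 0.9 | 58% | 66% |
| A quarter | 0.7 | 85% | 87% |
| A quarter | 0.9 | 63% | 68% |

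A repeat of these simulations agreed to within about 3 points. The loss is roughly 5 to 20 points if half to all are re-catheterised first, and 2 to 5 if a quarter are.

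Ranking last can also cost power. In a separate simulation (control median 3 h, log-SD 0.6, times 15% shorter on ICCAUT, 10% non-voiders in each arm), power was 70% with them left out and 57% with them ranked last.

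**The case against.** **Harm would be hidden.** A reader might infer this, but the documents do not support it for the trial as a whole. The primary table in SAP 6.5.1 shows secondary catheterisation and its retention subset by arm with confidence intervals, in all three analysis sets. These patients are also primary events.

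**The residual endpoint contradicts itself, because criterion-1 patients hold more than 200 ml.** That goes too far. The endpoint is defined after a first void, and bladder volume in someone who has not voided is not a post-void residual. The definition is incomplete, and its denominator is unstated.

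**The plan itself expects criterion-1 patients without a residual.** SAP 6.5.2.2 mentions absent residual data, but it concerns re-catheterisation for reasons other than retention. SAP 6.3.2 covers any missing residual, including a scan not done in time. Neither singles out these patients.

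**The rule was deliberate and the stakes are secondary.** The amendment rationale says secondary endpoints are not the main objectives, and the named secondary objective is urinary tract infection. This limits the importance of the point but does not supply the missing rule.

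**Not everyone beyond 10 h is lost.** This stands. Criterion 1 also needs the percussion finding and the ultrasound volume, so some patients void later and keep an observed time. Criterion-2 patients have voided and can have both values.

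**Counting non-voiders makes the residual endpoint a composite that overlaps the catheterisation row.** This also stands, and the relabelling and supportive analysis below are meant to meet it.

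**Conclusion.** The concern holds for two secondary endpoints. Followed as written, the plan compares time to first urination and residual above 200 ml only among patients who voided. That can shrink a benefit, or understate harm, in those two results.

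The size cannot be fixed from the documents. Under the stated assumptions, the missed risk difference is about −0.9 to −3.1 points at ratio 0.754 and −1.9 to −6.4 at ratio 0.5. All but the largest of these are small against a half-width of about 8 points. The effect is near zero when non-voiding is rare or equal between arms. For time to first void, the power loss is about 5 to 20 points in the less favourable scenarios, and with equal non-voiding, ranking last may itself lower power.

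The primary endpoint and the infection endpoint are untouched. Because the non-voider rate is unknown, the rule should be fixed before results are seen by arm.

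**What to change.** In SAP 6.5.3:

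- **(a) Time to first urination.** Give patients re-catheterised for retention before any void one common value ranked after every observed time in the Mann-Whitney/Hodges-Lehmann analysis. Report the percentage voiding before re-catheterisation by arm.
- **(b) Residual above 200 ml.** Keep these patients in the denominator and count them as positive. Label the endpoint as residual above 200 ml after first void, or re-catheterised for retention before voiding.
- **(c) Supportive results.** Report both endpoints among voiders with denominators stated. List patients re-catheterised before voiding for non-retention reasons as missing.

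The matching no-imputation sentences in SAP 6.3.2 and Protocol 11.3.2 and 11.4.3 need a cross-reference.

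**Cost.** Two derivation rules and some wording. The reason for and time to second catheterisation, and the time to first urination, are already on the CRF (Protocol 12.1), so no new data are needed. The time result becomes a rank comparison that includes failures rather than hours among voiders, and the residual endpoint partly overlaps the secondary-catheterisation row.

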6.1.2 Intervention

On the day following surgery (postoperative day 1) at 9:00 am, the nurse will perform the corresponding intervention operations for patients in both groups based on the group assignment indicated in the randomization envelope. Before the intervention, both groups of patients must complete the CRBD (Catheter-Related Bladder Discomfort) grading assessment by the assigned nurse (Appendix 3). During the patient's first catheterization, the use of selective α 1-adrenergic receptor blockers (such as tamsulosin) is not permitted.

1) The ICCAUT strategy included intermittent urethral catheter clamping and active urination training. In the ICCAUT group, intermittent catheter clamping was initiated at 9:00 am on the first postoperative day. In each cycle, the catheter was clamped for 3 h, followed by a 5-min release. The next cycle began as soon as the previous cycle had been completed. Catheter training concluded at 10:00 pm on the first postoperative day, and the catheter was left open during the night. The urinary catheter was removed on the second postoperative day, and the training did not stop until the catheter had been removed. During the training period, if the patient experienced a strong urge to urinate before the 3-h clamping time was over, the clamping could be released in advance for 5 min, allowing the patient to proceed to the next cycle of bladder training. Each time the catheter was released, the patients were encouraged to actively initiate urination to facilitate complete bladder emptying. We refer to this catheter management strategy, which involves intermittent clamping of the catheter and active urination during the release periods, as the ICCAUT

management strategy.

2) For patients in the free-draining group, no intervention was performed using a catheter during this period. The urinary catheter was removed at 9:00 am on the second postoperative day.

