3) Before the urinary catheter is removed on the second day, both groups of patients must complete the CRBD (Catheter-Related Bladder Discomfort) grading assessment again by the assigned nurse (Appendix 3), and urine samples must be collected for urinalysis and urine culture. Additionally, patients in the ICCAUT group must scan a code to fill out the Bladder Training Quality Self-Assessment Form (Appendix 4) before the catheter is first removed. After the catheter is removed, the time from the first catheter removal to the first urination, as well as the volume of the first urination, should be recorded for both groups of patients.

4) Immediately after the first urination, a bladder ultrasound must be performed to assess the residual urine volume in the bladder. The bladder ultrasound is conducted by a fixed radiologist from the ultrasound imaging department, who is exclusively assigned to our department and is located in the same therapeutic area as the patient. After the urinary catheter is removed, the patient must be observed and the situation of any secondary catheterization must be recorded. The observation period is the following 7 days after first urinary catheter removal. For patients who undergo secondary catheterization, the time from the first catheter removal to the secondary catheterization, the volume of urine drained after secondary catheterization, the method of secondary catheterization, and the reason for secondary catheterization must be recorded.

5) Record the IPSS score and ICIQ-SF score of the patient on the day following the first catheter removal (excluding patients who underwent secondary catheterization). Record complications within 30 days after surgery and their Clavien-Dindo classification (Appendix 5).

6.1.3 Discharge and follow-up.

After discharge, when the patient returns for a follow-up visit one month after

surgery, the physician must collect information on complications and their grading within the first postoperative month, and conduct an assessment using the one-month postoperative urinary function score form.

Table 1: Study Enrollment, Intervention, and Outcome Assessment Form

Item	Time point	Study phase		
		Surgery and Recruitment randomization		Post-randomization
		t	n	
Enrollment:				
Screen suitable population			X	
Informed consent			X	
Baseline and surgery-related data collection		X		X
Randomization			X	
Intervention:				
ICCAUT group				X
Free-drainage group				X
Assessment:				

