6.1 General calculation rules

All statistical tests were 2-sided, and statistical significance was set at $P < 0.05$. All statistical analyses were performed using R or SPSS. P-values will be quoted to three decimal places. Confidence intervals (CI) will be two-sided and 95% CI will be quoted to one decimal place.

Categorical variables will be reported as frequencies and percentages. Percentages will be quoted to one decimal place. Chi-square tests in contingency tables will be replaced by Fisher's exact tests if any expected cell frequency is less than five. Absolute risk differences and the corresponding 95% CI will be calculated.

Continuous data with normal distribution were presented as mean (standard deviation) and analyzed by Student's t-test. Continuous variables with non-normal distribution were reported as medians (quartile) and compared using the Mann-Whitney U test. Hodges-Lehmann method will be used to calculate the difference in median and the corresponding 95% CI. Data will be quoted to one decimal place.

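### The SAP gives the ordered four-level CRBD grade a risk difference with no cut-point, does not say which of two assessments is the endpoint, and would test it without using grade order or the pre-training grade

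*SAP*

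**What the plan says.** **The scale.** Protocol Appendix 3 defines four grades of rising severity, from no discomfort (0) to discomfort with behavioural reactions that need restraint (3).

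**The assessments.** Protocol v2.0, 6.1.2 schedules two, in both arms. The first is on postoperative day 1: "Before the intervention, both groups of patients must complete the CRBD (Catheter-Related Bladder Discomfort) grading assessment by the assigned nurse". The second comes before catheter removal on day 2: "both groups of patients must complete the CRBD (Catheter-Related Bladder Discomfort) grading assessment again by the assigned nurse".

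**The endpoint.** SAP 4.2 names only the CRBD grade. The table in SAP 6.5.3 types it as "categorical variable: level 0, level 1, level 2, level 3", with an absolute risk difference (95% CI) as effect size and one P value. It states no time point, whereas the ICIQ-SF and IPSS rows do. The baseline lists in SAP 6.4.1 and 6.4.2 contain no CRBD grade, and 6.5.3 contains no baseline adjustment.

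**The test.** The CRBD row names none. The general rules in SAP 6.1 say, for categorical data, "Chi-square tests in contingency tables will be replaced by Fisher's exact tests if any expected cell frequency is less than five", followed by "Absolute risk differences and the corresponding 95% CI will be calculated". The rank test is kept for another data type: "Continuous variables with non-normal distribution were reported as medians (quartile) and compared using the Mann-Whitney U test".

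**The concern.** A risk difference needs a binary event. In the same table the SAP fixes one for complications (Clavien-Dindo III or above) and for residual urine (above 200 ml), but not for CRBD. Two possible assessments and three possible cut-points are left to the analyst, although SAP section 1 says the plan was written in advance to avoid bias from the choice of analysis method.

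The likely test spreads its sensitivity over three degrees of freedom, when the scale is ordered and a general rise or fall in discomfort is the natural question. The pre-training grade, collected from everyone, is left out.

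At stake is the reading of one secondary endpoint. Protocol v2.0 gives reasons to expect an effect in either direction: section 1 cites evidence that active voiding eases catheter pain, and 11.2.1 foresees patients who cannot tolerate clamping. A real change could be reported as no difference.

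**Working it through.** **1. Sample size available.** The documents give no power calculation for CRBD, so the size comes from the primary endpoint (Protocol 11.1: 44.7% vs 59.3%, two-sided 0.05, power 80%). With unpooled variance:

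n = (1.960 + 0.842)² × (0.447×0.553 + 0.593×0.407) / 0.146² = 7.849 × 0.4885 / 0.02132 ≈ 180 per arm

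180 / 0.90 = 200, so the plan's figures reproduce. I use 180 evaluable per arm and two-sided 0.05 (SAP 6.1).

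**2. Assumptions.** The documents give no CRBD distribution, effect or correlation between the two assessments. Assumed: control grades 30/40/20/10%; a latent normal scale shifted by 0.25 SD in one direction; latent correlation between assessments of 0.3, 0.5 or 0.7.

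**3. What the missing cut-point does.** The control cut-points are −0.524, 0.524 and 1.282. After the shift, P(grade ≤ k) = Φ(cut-point − 0.25) = 0.219, 0.608 and 0.849. The same effect then gives three different risk differences:

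| Event | Control | Shifted arm | Difference |
|---|---|---|---|
| Grade 1 or above | 70.0% | 78.1% | 8.1 points |
| Grade 2 or above | 30.0% | 39.2% | 9.2 points |
| Grade 3 | 10.0% | 15.1% | 5.1 points |

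**4. Power by simulation, 180 per arm.** Compared: the Pearson chi-square on the 2×4 table (3 df); the midrank Wilcoxon test, which is the score test of the proportional-odds model; and regression of the midranks on arm and pre-training grade, standing in for the adjusted ordinal model (sex and APR were not simulated).

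| Analysis | Power |
|---|---|
| Unordered chi-square | about 42% |
| Ordered test, no baseline | about 59% |
| Ordered, with pre-training grade, correlation 0.3 | about 61% |
| Same, correlation 0.5 | about 68% |
| Same, correlation 0.7 | about 78% |

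Type I error is about 5% for all.

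**5. Sensitivity to the assumed grades.** Unordered vs ordered power at 180 per arm, with a common odds ratio (OR) as the effect:

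| Assumed control grades | OR 1.5 | OR 1.75 | OR 2.0 |
|---|---|---|---|
| 40/35/20/5% | 38.8 vs 55.5% | 67.5 vs 82.5% | 86.5 vs 94.6% |
| 60/25/12/3% | 35.4 vs 51.1% | 63.4 vs 79.4% | 83.4 vs 93.1% |
| 25/40/25/10% | 39.4 vs 55.8% | 68.2 vs 83.2% | 86.7 vs 94.9% |

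The loss is about 15 to 17 points at odds ratios of 1.5 to 1.75 and about 8 to 10 points at 2.0.

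**6. Where the ordered test fails.** Take 40/35/20/5% against 47/20/26/7%, with more patients at both ends in the second arm. The chance that a second-arm patient has the higher grade is 0.40×0.53 + 0.35×0.33 + 0.20×0.07 = 0.3415. Half the chance of a tie is ½(0.40×0.47 + 0.35×0.20 + 0.20×0.26 + 0.05×0.07) = 0.1568. The sum is 0.498, almost exactly one half, so a rank test sees nothing. Simulated power at 180 per arm: chi-square 78%, rank test 5%, grade-2-or-above dichotomy 39%.

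**The case against.** **The table is a shell.** It lists the type of effect size per variable, SAP 6.1 uses the plural for risk differences, and the primary-endpoint table gives each sub-row its own difference. One difference per grade is therefore a fair reading, and the analysis is not impossible. This stands: the fault is an unstated rule.

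**The unordered test is inferred.** It follows from the general rule, because the CRBD row names no test. This stands too, but the other reading, that no test is specified, also needs repair.

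**A reader might infer that the planned test is the least sensitive option.** That is not so. With the 30/40/20/10% grades at 200 per arm, the chi-square has 47% power and the grade-2-or-above dichotomy 49% for a shift upward; both have 45% for a shift downward. For a non-monotone effect the chi-square is far better than the ordered test, and mixed effects are plausible given the protocol's own expectations.

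**The pre-training grade is not a clean baseline.** Under Protocol v2.0, 5.1.2 the nurse receives the envelope before 8:00 am on day 1 and opens it. Under 6.1.2 that nurse grades CRBD before the 9:00 am intervention. Section 5.2 says neither nurse nor patient is blinded. The grade thus precedes the intervention but apparently follows allocation, and may reflect knowledge of the arm. The unadjusted comparison is valid; adjustment buys precision only.

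**A reader might extend the full criticism to the IPSS and ICIQ-SF classes, or call discomfort the main trade-off of clamping.** The raw IPSS and ICIQ-SF scores already have a Hodges-Lehmann analysis in SAP 6.5.3. The harm that the trial names as its secondary objective is urinary tract infection; CRBD is one of six secondary endpoints.

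**Conclusion.** The concern holds for CRBD. The risk difference lacks a cut-point or per-level rule, the endpoint assessment is not identified, and the general rule leads to a test that discards grade order while the collected pre-training grade goes unused.

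For a one-directional effect the loss from ignoring order is about 17 power points in the main scenario (42% vs 59%) and about 8 to 17 across the other distributions tried. Adding the pre-training grade gains about 2, 9 and 19 further points at correlations of 0.3, 0.5 and 0.7, so little is gained if the two assessments are weakly related. All of these sizes rest on assumed inputs, and the direction reverses for a non-monotone effect.

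The planned comparison remains valid: type I error is not inflated and the primary conclusion is untouched. For the IPSS and ICIQ-SF classes, only the missing cut-point for the risk difference carries over.

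**What to change.** In SAP 4.2 and 6.5.3:

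- Name the grade taken before catheter removal as the CRBD endpoint.
- Analyse it with a proportional-odds model containing arm, sex, APR (the two stratification factors in SAP 2.2) and the pre-training grade. Report the common odds ratio with 95% CI.
- Show the same model without the pre-training grade, with a note on when and by whom that grade is taken.
- Tabulate counts per grade by arm, and give one prespecified risk difference with 95% CI for grade 2 or above.
- For the IPSS and ICIQ-SF classes, state the cut-point to which the risk difference refers.

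The cost is SAP wording only, since the protocol already collects every item; the change should be made before outcomes are compared by arm. The price is a proportional-odds assumption and low power for non-monotone effects, which the grade counts and the fixed dichotomy help to reveal.
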